10.2 Sensitivity Analyses for the Primary Efficacy – Missing Not at Random

The primary efficacy analysis (MMRM) relies on the assumption that the missing data mechanism follows the missing at random (MAR) scenario. In this case, it is assumed that the reason for data being missing may depend on observed data, but not on the unobserved missing data. The likelihood-based MMRM analysis is an appropriate method for the statistical analysis under MAR assumption.

The following 2 sensitivity analysis models, which are within the pattern-mixture model framework, will be used to examine the robustness of the primary efficacy analysis results for the missing not at random (MNAR) mechanisms. Under MNAR, it is assumed that the reason for data being missing is related to the unobserved missing data.

Model 1: Placebo Multiple Imputation

Rationale: The imputations are based on the distribution of placebo group responses over time. The underlying assumption is that the missing data for a subject on the active treatment follow the distribution of the placebo responses, i.e., the mean values and intra-subject correlations based on the placebo responses will be applied.

The model is implemented in 3 steps: 1) imputations, 2) analysis of complete data sets, and 3) inference. Sample SAS codes are provided in [Appendix 2](#).

Step 1: Imputations

A total of 200 sets of posterior mean and co-variance estimates are extracted from the SAS MI procedure using the available non-missing placebo data. One hundred of the posterior sets will be applied to the pooled active treatment group, while the other 100 will be applied to the placebo group. One set of imputations for all missing values will be generated based on each variation of posterior estimates. All 100 datasets for imputations within a treatment group will be ordered from 1 to 100 and combined between pooled active treatment group and placebo, for a total of 100 completely imputed datasets.

Step 2: Analysis of Complete Datasets

The primary efficacy endpoint will be analyzed for each of the 100 complete datasets with imputed data using an analysis of covariance with treatment group as factors and the baseline value as a covariate.

Step 3: Inference

The LS mean difference estimates will be averaged, and the associated SEs will be summarized based on within-imputation and between-imputation variance using the SAS MIANALYZE procedure to yield a final estimate with associated 95% CI and p-value.

If the primary efficacy criterion is met at the interim analysis, then the above process will be adjusted. For subjects who are ongoing at the time of study stop, the posteriors from the corresponding treatment group will be applied. For dropouts at the time of the interim analysis, the placebo posteriors will be applied.

Model 2: Multiple Imputations with Penalties Applied to Dropouts

Rationale: The underlying assumption is that subjects who dropout performing worse than MAR by a penalty.

The model is implemented in 3 steps: 1) imputations and application of penalty, 2) analysis of complete data sets, and 3) inference. Sample SAS codes for steps 1a and 1b are provided in

Step 1a: Imputations

Missing data will be multiply imputed for 100 times on a treatment specific, multivariate normal distribution of the response overtime, using the SAS MI procedure with treatment in the BY statement. This step is based on the MAR assumption.

Step 1b: Application of Penalty

A penalty will then be applied to the multiply imputed values at the last scheduled visit (Visit 6). The penalty will be a fraction of the estimated SD for the primary efficacy endpoint (the square root of the estimated element for the last scheduled visit of the co-variance matrix R from the primary MMRM model): (0*SD), (0.25*SD), (0.5*SD), etc.

Step 2 (analysis of complete data sets) and Step 3 (inference) are the same as Step 2 and Step 3, respectively, for Model 1.

If the primary efficacy criterion is met at the interim analysis, then the penalties will only apply to dropouts. Multiply imputed values for ongoing subjects at the time of study stop will be used in the analysis without penalties.

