2.5 Determination of Sample Size

Approximately 245 subjects will be screened to randomize approximately 195 subjects in a 5:5:5:5:6 ratio to SPD489 5, 10, 20, 30 mg or placebo to achieve 156 completers for the study (30 in each active treatment group and 36 in the placebo group) and 85% power for the primary efficacy analysis at a 2-sided 0.05 significance level.

The sample size planned at study initiation is estimated based on the primary comparison between SPD489 10, 20, 30 mg pooled together (excluding the 5mg) compare with placebo on the primary efficacy endpoint, in a group sequential design with 1 interim analysis using the Lan-DeMets alpha spending function with O'Brien-Fleming boundary for the primary efficacy endpoint. Assumptions for the calculation include the true mean difference of 8.4 with the common standard deviation (SD) of 14 for the primary efficacy endpoint, for an effect size of 0.6, and a dropout rate of 20%.

In order to maintain sufficient study power to detect a clinically meaningful treatment effect for the primary efficacy endpoint, a blinded sample size re-estimation is planned. If the study continues beyond the proposed interim analysis, or if the interim analysis is waived, then the sample size re-estimation will be performed when approximately 75% of the 195 subjects have either completed or discontinued from the study. In this case, cumulative primary efficacy data will be used to estimate a pooled common SD to ensure the variability hypothesized at the design stage is not underestimated. Together with the assumed treatment difference of 8.4, the final total number of subjects to be enrolled will be calculated using the re-estimated pooled SD ([Friede and Kieser 2006](#)). Step by step details for estimating the pooled SD are included in the [Appendix 1](#). Using the pooled common variance estimated to do a blinded sample size re-estimation does not inflate the Type I error.

The final total sample size could potentially be as high as 218 completers, which corresponds to the 97.5% percentile of the distribution of the estimator on the assumed true common SD of 14 postulated at the design stage. If the re-estimated pooled common SD is larger than 14, the sample size will be increased. Otherwise, the sample size will remain the same. Note that the total of 218 completers is not considered a cap. As the final sample size is data driven, a higher number, though unlikely, is possible.

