20.2 Appendix 2 Sample SAS Codes

Mixed Model Repeated Measures (MMRM)

```
proc mixed /* select derived dataset */;
  class trt subjid visit;
  model chg = trt visit trt*visit base base*visit / ddfm=kr;
  repeated visit / subject=subjid type=UN;
  /* LSmean, Estimate and/or LSMestimate statement(s) */
  /* Data output or object delivery statement(s) */
Run;
```

Missing Not at Random (MNAR) Sensitivity Analysis

Model 1 - Placebo Multiple Imputation

```
*Step 1;
proc mi data=unimputed out=discard nimpute=200 seed=347 noprint;
  where treatment=1; *where 1 is placebo;
  var baseline chy1-chy7
  mcmc outset=posteriors; *picks up the placebo posteriors;
run;

*100 posteriors for the placebo, rest for active;
data posteriors(type=est);
  set posteriors;
  if 1<=_imputation_<=100 then do; *assign placebo posteriors;
    treatment=1;
  end;
  if 100<=_imputation_<=200 then do; *assign posteriors to active;
    treatment=2;
    imputation_=_imputation_-100;
  end;
run;

proc sort data=unimputed;
  by treatment;
run;

proc mi data=unimputed out=imputed;
  by treatment;
  var baseline chy1-chy7;
  mcmc inest=posteriors; *use the placebo posteriors;
run;

*Step 2;
data endpoint;
  set imputed;
  endpoint=chy7;
run;
```

```
proc sort data=endpoint;
  by _imputation_;
run;

proc glm data=endpoint;
  by _imputation_;
  class treatment;
  model endpoint = baseline treatment / solution;
  estimate 'Active vs Placebo' treatment -1 1;
ods output estimates=est;
run;

*Step 3;
proc sort data=est;
  by label _imputation_;
run;

proc mianalyze data=est;
  by label;
  modeleffects estimate;
  stderr stderr;
run;
```

Model 2 - Multiple Imputations with Penalties Applied to Dropouts

*Note: dataset "unimputed" has one row per subject, repeated measures are structured in columns;

```
*Step 1;
data unimputed;
  set unimputed;
  missing=(chg4=.);
run;

proc sort data=unimputed;
  by treatment;
run;

proc mi data=unimputed out=imputed nimpute=200 seed=347 noreport;
  by treatment;
  var baseline chy1-chy7;
run;

%let SD=10;
* This will be replaced by the estimated SD[chg7] from the MMRM co-variance matrix R
  (use R or RCORR option in REPEATED statement under PROC MIXED);

%let penalty=0.25*&SD;
* Repeat this step for various values (0.25, 0.5, etc) as per SAP;

data imputed;
```

```
set imputed;
if missing then chg7=chg7 + &penalty; * + or - , depending on the measure;
run;
```

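### SAP 10.2 Model 2 penalises dropouts in both arms, so it may say little about how badly active-arm dropouts could do before the result fails; its sample code also flags the wrong visit

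*SAP*

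**What the plan says.** SAP 10.2 tests the primary mixed model against data missing not at random with two models.

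Model 1 imputes from placebo: "The underlying assumption is that the missing data for a subject on the active treatment follow the distribution of the placebo responses".

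Model 2 first imputes within treatment under MAR and then worsens the imputed values. Its rationale reads: "The underlying assumption is that subjects who dropout performing worse than MAR by a penalty". Step 1b says: "A penalty will then be applied to the multiply imputed values at the last scheduled visit (Visit 6". On size it says "The penalty will be a fraction of the estimated SD for the primary efficacy endpoint", with the list "0*SD), (0.25*SD), (0.5*SD), etc". No arm is named or excluded, and no stopping point is given for the list. After an interim stop the penalty is confined to dropouts: "Multiply imputed values for ongoing subjects at the time of study stop will be used in the analysis without penalties". That rule separates dropouts from ongoing subjects, not active from placebo.

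The sample code in SAP 20.2 applies the penalty with "if missing then chg7=chg7 + &penalty;", again with no condition on treatment. The flag it uses is set where `chg4` is missing. SAP 10.3 reuses both models for CGI-I.

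**The concern.** A reader expects a penalty analysis to show how much worse than MAR the treated dropouts could have done before the conclusion fails. When the same penalty falls on both arms, the two effects offset each other in the treatment contrast. If dropout is balanced, or heavier on placebo, a result that holds across the penalties could be read as robustness when the active-arm assumption has hardly been tested.

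The code is a separate matter. A flag on one visit and a penalty on another would, if copied, penalise a different set of subjects from the one in SAP 10.2.

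**Working it through.** **Inputs.** SAP 2.5: true difference 8.4, SD 14, "a dropout rate of 20" percent, 30 completers per active arm (90 pooled over 10, 20 and 30 mg) and 36 on placebo. SAP 2.6.2: final boundary 0.0477. The difference is written as a benefit, so a larger number favours the drug.

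**The plan's own figures.** SE = 14 × √(1/90 + 1/36) = 2.76. Then 8.4/2.76 = 3.04, and by normal approximation power is 0.861 at 0.05 and 0.856 at 0.0477, against 85% stated. Also 156/0.8 = 195. Both reproduce.

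**Formulas.** Let k be the penalty in SDs, and mA and mP the shares of subjects with a penalised (imputed) Visit 6 value in the pooled active group and on placebo.

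- Both arms: estimate = 8.4 − 14 × k × (mA − mP).
- Active only: estimate = 8.4 − 14 × k × mA.
- Variance by the multiple-imputation rules, ignoring information from earlier visits. Within = pooled variance × (1/nA + 1/nP), where a penalised arm has variance 196 × (1 + m(1 − m)k²). Between = 196 × (1/observed − 1/n), summed over arms.
- The tipping k is where estimate/SE falls to the two-sided 0.0477 critical value, about 2.00.

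**Balanced case.** nA = 90/0.8 = 112.5, nP = 36/0.8 = 45, m = 0.20 in both arms, assuming no dropout has a usable Visit 6 score.

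- At k = 0: within = 196 × (1/112.5 + 1/45) = 6.10; between = 196 × (1/90 − 1/112.5 + 1/36 − 1/45) = 1.52; SE = √7.62 = 2.76.
- Both arms, k = 1: estimate 8.4; SE = √(6.10 × 1.16 + 1.52) = 2.93.
- Both arms, k = 3.2: estimate 8.4; SE = √(6.10 × 2.64 + 1.52) = 4.20; ratio 2.00.
- Active only, k = 0.95: estimate 8.4 − 14 × 0.20 × 0.95 = 5.74; SE 2.87; ratio 2.00.

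**Range over the imputed shares.** The documents give one overall dropout rate. All the other shares below are assumptions.

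| Imputed share, active / placebo | Penalty on | k = 0.25 | k = 0.5 | k = 1 | Tipping k, about |
|---|---|---|---|---|---|
| 20% / 20% | both | 8.4 | 8.4 | 8.4 | 3.2 |
| 20% / 20% | active | 7.7 | 7.0 | 5.6 | 0.95 |
| 10% / 10% | both | 8.4 | 8.4 | 8.4 | 4.5 |
| 10% / 10% | active | 8.05 | 7.7 | 7.0 | 1.9 |
| 25% / 15% | both | 8.05 | 7.7 | 7.0 | 1.5 |
| 25% / 15% | active | 7.5 | 6.65 | 4.9 | 0.8 |
| 15% / 25% | both | 8.75 | 9.1 | 9.8 | 17 |
| 15% / 25% | active | 7.9 | 7.35 | 6.3 | 1.2 |

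The 10% rows stand for half of the dropouts having an early-termination score analysed as Visit 6. Simulation of the 20%/20% case (1,500 trials, 50 imputations) agrees: 83% of trials are significant at k = 0. At k = 0.5 and 1, both-arm penalties leave 83% and 80%, and active-only penalties 67% and 47%.

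**Direction of dropout.** Protocol 4.4.2 lists lack of efficacy as a reason to discontinue, and Protocol 6.2.3 discontinues subjects who cannot tolerate the product. The first could load placebo and the second the active arms. The documents do not say which to expect.

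**The flag.** SAP 10.2 penalises imputed Visit 6 values; the code penalises `chg7` where `chg4` is missing.

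- A subject who leaves after the `chg4` visit has an imputed endpoint that is not penalised.
- A subject who misses only that visit has an observed endpoint that is penalised.
- No condition separates ongoing subjects from dropouts, as the interim-stop rule requires.

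If `chg4` is Visit 4 and dropouts are last seen evenly over Visits 1 to 5 (both assumptions), those last seen at Visits 4 and 5 escape: 2/5 = 40%. With equal dropout and timing in both arms, the expected both-arm estimate is unchanged. At 25%/15% and k = 1, the shift falls from 14 × 0.10 = 1.4 to 0.6 × 1.4 = 0.84 points.

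**The case against.** The strongest reply is that nothing in Model 2's text is wrong. Dropouts in any arm may do worse than MAR predicts, and SAP 10.2 promises to examine robustness, not to find an active-arm tipping point. Model 1 already treats active-arm dropouts unfavourably. This stands as far as it goes: the both-arm version is legitimate and should stay. But Model 1 is one fixed scenario and cannot show how far the active-arm assumption can be pushed.

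A reader might infer that Model 2 can never overturn the result, or always favours the drug. Neither follows. The SE grows with k, so significance can be lost with no shift at all, and with heavier active dropout the both-arm version does work against the drug, though more weakly than an active-only penalty. Nor is the penalty capped at 0.5 SD: the list is open-ended. The gap is the lack of a stopping point, not a ceiling.

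The effect may also be small. Protocol 7.1.2.3 asks subjects who discontinue early to complete Visit 6/ET. If half of dropouts supply a usable score, simulated significance at k = 0.5 is 87% with both arms penalised and 83% with active only.

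Finally, the code is labelled as a sample, holds a placeholder SD, and uses seven change columns for six post-baseline visits. The SAP text is clear that Visit 6 is what counts. That limits the seriousness of the flag, but SAP 10.2 points to this code for Steps 1a and 1b, so it is likely to be copied.

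**Conclusion.** The point holds, at minor severity. As written, Model 2's expected estimate moves by k × SD × (active minus placebo share of penalised values): not at all with balanced dropout, towards the drug if placebo dropout is higher, and against it if active dropout is higher. At planning values the both-arm version loses significance at about 3.2 to 3.3 SD (the upper figure by normal approximation), against about 0.95 SD for an active-only penalty. Model 2 may therefore say little about how much worse active-arm dropouts could do.

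These figures assume a true effect of 8.4, SD 14, 20% imputed in each arm and no gain from earlier visits. Less missing data raises both tipping points.

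The sample-code flag is wrong as written, because it contradicts SAP 10.2. It leaves the expected both-arm estimate alone when dropout and its timing are equal, and dilutes the shift when dropout is unequal.

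A reader might go further and doubt the primary test or the type I error. The documents do not support that: under SAP 2.6.2 only the primary efficacy result decides whether the criterion is met.

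**What to change.** 1. In the SAP 20.2 sample code, set the flag on a missing (imputed) Visit 6 value. After an interim stop, set it only for subjects who discontinued, as SAP 10.2 requires.
2. Reconcile Model 2's heading and rationale, which speak of dropouts, with Step 1b, which speaks of imputed values. They differ for a subject who stays in the study but has no Visit 6 score, for example through missing items (SAP 18.2.1). State whether that subject is penalised.
3. Keep the both-arm version and say that it covers both arms. Add a version that penalises only the pooled 10, 20 and 30 mg group, with placebo imputed under MAR, in steps of 0.25 SD until significance is lost. Report the tipping point.
4. As housekeeping, align the number of imputations (100 in the text, 200 in the Model 2 code) and the number of visit columns.

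The cost is a few lines of SAP text and code before unblinding, with no further data or alpha. The downside for the sponsor is that the reported sensitivity result may look less favourable.

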10.3 Key Secondary Efficacy Endpoint and Analysis

The key secondary efficacy endpoint CGI-I provide an overall assessment of global symptom improvement. It will be analyzed using the same analysis method (MMRM) as for the primary efficacy endpoint. The baseline CGI-S score will be used as the covariate. The contrast of interest will be at Visit 6 (Week 6) for the pooled SPD489 group compared with placebo.

The CGI-I will be analyzed using the 2 sensitivity analysis models described in Section 10.2 to examine the robustness of the key secondary efficacy analysis (MMRM) results.

10.4 Dose-response Analyses

The primary and key secondary efficacy analyses, and dose-response analysis will be conducted separately, and therefore no multiplicity adjustment will be considered for these objectives together.

[figure not shown]
In this section all analyses will be performed on DRAS using R MCPMod package, and treatment arms 0 mg (placebo), 5, 10, 20, 30 mg (SPD489) will not be pooled.

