### **6.2.3 Dosing**

Dosing should begin at approximately 7:00AM ( $\pm 2$  hours) on the morning after the baseline visit (Visit 0). Subjects will be instructed to take 1 capsule daily in the morning throughout the study, at approximately the same time each day. The same parent/LAR should be available daily to dispense the dose of investigational product for the study duration.

SPD489 may be administered in one of the following ways:

- Swallow SPD489 capsule whole, or
- Open capsule, empty and mix the entire contents with yogurt, water, or orange juice.

The contents should be mixed until completely dispersed. The subject must ingest the entire amount of the mixture immediately within 3 minutes. The subject should not take anything less than one capsule per day and a single capsule cannot be split. The empty gelatinous capsule should be discarded into a trash receptacle by the parent/LAR.

Subjects will begin dosing with the lowest strength of SPD489 (5 mg) and will be titrated until the randomly assigned fixed-dose is reached.

Once subjects reach the fixed-dose level, this dose will be maintained until the end of the study.

No dose reductions are permitted during the study. Subjects who are unable to tolerate investigational product will be discontinued.

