4.4 Full Analysis Set

The Full Analysis Set (FAS) will consist of all subjects in the Safety Analysis Set who have at least 1 post-dose ADHD-RS-IV-Preschool Version Total Score assessment.

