4.5 Dose-response Analysis Set

The Dose Response Analysis Set (DRAS) will consist of all subjects in the Safety Analysis Set who have at least 1 valid primary efficacy measurement (ADHD-RS- IV Preschool Version Total Score) on the randomized target dose level of the investigational product.

The above analysis sets will be utilized for both the interim and the end of study analyses.

Subjects are randomized at baseline (Visit 0) in a 5:5:5:5:6 ratio to SPD489 5, 10, 20, 30 mg or placebo group. If not stated otherwise, each dose strength and pooled doses (10, 20, 30 mg pooled together) will be used for reporting the study variables, as below.

| Parameter | Placebo | SPD489 | | | | |
|--------------------------|---------|--------|------|------|------|----------------------------|
| | | 5mg | 10mg | 20mg | 30mg | Pooled 10, 20, 30 mg |
| Baseline Characteristics | ✓ | ✓ | ✓ | ✓ | ✓ | ✓ |
| Primary Efficacy | ✓ | | | | | ✓ |
| Key Secondary Efficacy | ✓ | | | | | ✓ |
| All Other Efficacy | ✓ | | | | | ✓ |

| Parameter | Placebo | SPD489 | | | | |
|----------------------------|---------|--------|------|------|------|----------------------------|
| | | 5mg | 10mg | 20mg | 30mg | Pooled 10, 20, 30 mg |
| Dose-response Relationship | ✓ | ✓ | ✓ | ✓ | ✓ | ✓ |
| Safety Reporting | ✓ | ✓ | ✓ | ✓ | ✓ | ✓ |

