10.4.4 Additional Analyses

A line-plot of mean change from baseline with 95% CI for each randomized treatment group will be generated.

Each SPD489 arm will be compared with placebo in ADHD-RS-IV Preschool Version Total Score change from baseline using MMRM. The comparisons will be conducted in a sequential order for adjusting for the multiplicity, which will test the highest dose level, 30 mg, first. The model structure will be similar to the primary efficacy analysis. However, this analysis is not powered for the comparisons.

A sigmoid nonlinear E_{max} model ([MacDougall, J. 2006](#)) below will be fitted, and the sigmoid E_{max} model curve will be plotted.

$$R_i = E_0 + \frac{D_i^m \times E_{max}}{D_i^m + ED_{50}^m} + \varepsilon_i$$

Where i = the subject indicator; R_i = dose response for subject i that measured as ADHD-RS-IV Preschool Version Total Score change from baseline; E_0 = the dose response when dose strength is 0 mg (placebo); D_i = the dose level for subject i ; m = the slope factor determining the steepness of the dose response curve ($m > 0$); E_{max} = the maximum possible effect for the investigational product; ED_{50} = The dose level, which produces half of E_{max} ; ε_i = the random error term for subject i .

For the E_{max} model evaluations, initial parameters will be set to $E_0 = 0$; $E_{max} = -19.5$; $ED_{50} = 15.0$ and $m = 3.17$. Where the m was calculated using the formula

$$ED_p = ED_{50} \left(\frac{p}{1-p} \right)^{1/m}$$

let $p = 0.9$, $ED_{90} = 30.0$.

The MCP-Mod methodology provides a flexibility of modeling for dose response relationship, while preserving the robustness to model misspecification associated with multiple comparison procedures (Bretz et al. 2005). However, if the MCP-Mod fails to converge to any pre-specified candidate curves, the sigmoid nonlinear E_{max} model, as a backup, will provide a dose response relationship. Using the relationship and clinically relevant threshold— 5.6 reduction from baseline in ADHD-RS-IV Preschool Version Total Score together, an approximately estimate of MED will be obtained.

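### As written, SAP 10.4 puts the single-dose versus placebo MMRM tests on the dose-response set, which removes early leavers from the 10, 20 and 30 mg arms but not from placebo

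*SAP*

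**What the plan says.** - **Analysis set.** SAP 10.4 opens its section with "In this section all analyses will be performed on DRAS using R MCPMod package". SAP 10 names the FAS only for the primary and key secondary analyses and their sensitivity analyses.
- **The tests.** SAP 10.4.4, inside that section, says: "Each SPD489 arm will be compared with placebo in ADHD-RS-IV Preschool Version Total Score change from baseline using MMRM". They run in sequence, "which will test the highest dose level, 30 mg, first". The SAP adds: "However, this analysis is not powered for the comparisons". It describes the model as similar in structure to the primary one and names no analysis set.
- **DRAS (SAP 4.5).** A treated child must have "at least 1 valid primary efficacy measurement (ADHD-RS- IV Preschool Version Total Score) on the randomized target dose level of the investigational product".
- **FAS (SAP 4.4).** A treated child must have "at least 1 post-dose ADHD-RS-IV-Preschool Version Total Score assessment". The rule is the same in every arm.
- **Titration (Protocol 6.2.3).** "Subjects will begin dosing with the lowest strength of SPD489 (5 mg) and will be titrated until the randomly assigned fixed-dose is reached". Titration takes three weeks with weekly visits (Protocol 7.1.2.1). Dose reduction is not allowed, and children who cannot tolerate the product are discontinued.
- **Reporting table (SAP 4.5).** Among the efficacy rows, single doses appear only under dose-response. All other efficacy rows are placebo against the pooled doses, so no FAS comparison of a single dose with placebo is planned elsewhere.

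**The concern.** DRAS membership is decided after randomisation, and how hard it is to qualify depends on the arm. A 5 mg child is on the assigned dose from the first capsule. A placebo child is too, in effect, although the SAP does not define a target level for placebo. A 30 mg child must first get through titration. If two children leave in week 2 for the same reason, the placebo child is analysed and the 30 mg child is not.

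The set also works against the model. SAP 10.2 justifies the MMRM by assuming that missingness may depend on observed scores. That protection holds only if those scores are in the model, and the DRAS deletes the early scores of exactly the children who left. MCP-Mod has a reason to ask for a rating at the target dose; an MMRM by randomised arm does not need one.

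At stake is the validity of the 10, 20 and 30 mg comparisons with placebo. The effect is largest for 30 mg, the first step of the test sequence.

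**Working it through.** **1. The plan's own figures.** SAP 2.5 gives a difference of 8.4, SD 14, 90 pooled against 36 placebo completers, 85% power and 20% dropout.

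- Power is 86.1% at two-sided 0.05 and 85.6% at the final nominal level of 0.0477.
- Randomised: 156 / 0.8 = 195. At 5:5:5:5:6 that is 195 × 5/26 = 37.5 per active arm and 195 × 6/26 = 45 on placebo.

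These agree with the SAP. It gives no figure for the single-dose tests. For 30 against 36 completers and a difference of 8.4, power is 68%, which fits the statement that they are not powered.

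**2. Assumptions not in the documents' text.** One titration step per weekly visit, so the first rating on target is at Visit 1, 2, 3 and 4 for 5, 10, 20 and 30 mg. SD rises from 10 to 14 over six visits, with AR(1) correlation 0.8 and no baseline covariate. Dropout is 20%. For response-related dropout, the log-hazard changes by 1 per SD of the last score.

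**3. Method.** 37 active against 45 placebo children, 3,000 simulated trials per case, no true drug effect. The Week 6 difference is the maximum-likelihood estimate from an unstructured repeated-measures model, first on all children (FAS), then without active children who lack an on-target rating (DRAS). Negative values favour the drug. Rejection means estimate / SD of the estimates < -1.96, nominally 2.5% one-sided. The Monte Carlo error of a mean is about 3.35 / √3000 = 0.06 points.

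**4. By dose, poor responders leaving, 20% dropout.**

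| Arm | Excluded by DRAS | FAS estimate | DRAS estimate | False positive, FAS | False positive, DRAS |
|---|---|---|---|---|---|
| 5 mg | 0% | 0.00 | 0.00 | 2.6% | 2.6% |
| 10 mg | 4.3% | 0.04 | -0.17 | 2.3% | 2.8% |
| 20 mg | 8.3% | 0.00 | -0.44 | 2.4% | 3.4% |
| 30 mg | 12.1% | 0.01 | -0.71 | 2.5% | 4.3% |

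**5. 30 mg, by reason for leaving (placebo dropout 20%).**

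| Who leaves the 30 mg arm | Active dropout | Excluded | FAS estimate | DRAS estimate | False positive, DRAS |
|---|---|---|---|---|---|
| Poor responders | 20% | 12.0% | 0.07 | -0.63 | 4.2% |
| Poor responders | 40% | 23.9% | -0.09 | -1.58 | 6.6% |
| Unrelated to response | 20% | 12.6% | 0.00 | 0.00 | 2.7% |
| Good responders | 20% | 12.0% | 0.04 | +0.77 | 1.3% |
| Good responders | 40% | 23.8% | -0.03 | +1.48 | 0.8% |

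**6. Other assumptions, dropout near the planned rate.** Varying the between-visit correlation (0.6-0.8), the strength of the link between score and dropout, and whether early-termination ratings keep week-4 leavers in the DRAS gives these ranges for 30 mg:

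- Excluded: 8-13%, or 0.08 × 37.5 = 3 to 0.13 × 37.5 = 5 children.
- Poor responders leaving: 0.6-1.5 points towards the drug; false positives 3.4-6.3%.
- Good responders leaving the 30 mg arm: about 0.8-1.1 points against the drug; false positives 1.0-1.7%.

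**7. Cross-check.** With a standard error near 3.35, a shift of b points towards the drug gives a false-positive rate of Φ(-1.96 + b/3.35). For b = 0.71 this is Φ(-1.75) = 4.0%; for b = 1.5, Φ(-1.51) = 6.5%; for b = -1.1, Φ(-2.29) = 1.1%. The simulated rates agree closely.

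**The case against.** **The sentence may not have been meant for these tests.** It ties the DRAS to the R MCPMod package, which does not fit an MMRM; SAP Appendix 2 gives the MMRM code in SAS. Protocol 9.8 links the DRAS to dose-response evaluation, and 10.4.4 points to the primary model, which uses the FAS. This stands as a doubt about intent. It does not settle the text: the sentence covers all analyses in the section, and similarity of model structure says nothing about population.

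**The exclusions may be fewer.** The protocol asks for the Visit 6/ET evaluations at discontinuation (4.4, 7.1.2.3), and SAP 10 keeps ratings up to 3 days after the last dose. A child who leaves soon after reaching the target dose can therefore still qualify. This stands and sets the lower end, about 8%.

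**The direction is open.** A reader might infer that the DRAS biases these tests towards the drug. The documents do not support that. Lack of efficacy is a listed reason for discontinuation (Protocol 4.4.2), but the rule tied to dosing and titration is intolerance, and intolerant children may have been responding well. The bias then reverses.

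**The effect is small and the tests are not decisive.** A shift of 0.6-1.5 points is about 0.2-0.4 standard errors (0.6/3.35 to 1.5/3.35). The confirmatory test pools 10-30 mg on the FAS, and the minimum effective dose comes from MCP-Mod. This stands too. The zero bias on the FAS also follows from simulating dropout that depends only on observed scores.

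**Conclusion.** The point holds as a minor one. On the text, the 10, 20 and 30 mg comparisons with placebo use a set that filters the active arms after randomisation and leaves placebo untouched.

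It would be too strong to say that all four tests are affected, since 5 mg children are on target from the first dose. It would also be too strong to say that these tests decide which doses work: they are labelled additional and unpowered, and the study-wise alpha control covers only the primary and key secondary endpoints. They are nevertheless ordered to adjust for multiplicity, so they are meant to be read as tests.

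The size for 30 mg in step 6 rests on 18-20% dropout and weekly titration steps, and its sign depends on who leaves. The 40% dropout rows show sensitivity only; the plan assumes 20%. What does not depend on these assumptions is that the filter is unequal between arms and that the MMRM does not need it.

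**What to change.** In SAP 10.4.4, state that the SPD489 dose-versus-placebo MMRM comparisons use the FAS by randomised arm, with all on-treatment ratings from Visit 1, as in the primary analysis. Limit the DRAS sentence in 10.4 to the MCP-Mod analyses (10.4.1-10.4.3). If the DRAS version of the comparisons is wanted, label it a sensitivity analysis. In SAP 4.5, say what the target level means for placebo.

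The cost is a sentence or two before unblinding, with no new data and no change in sample size. Individual-dose estimates may change slightly.
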